Detailed Protocol Title: Behavior and brain responses to drugs

NCT03964350 Unique Protocol ID: IRB19-0293

Date: 4/11/22

Detailed Protocol Title: Behavior and brain responses to drugs Date: Investigators: [name] Other personnel:

IRB19-0293

Summary: Alcohol abuse and dependence remain significant public health issue, and there is a need to identify risk factors predicting excessive alcohol use. We and others have demonstrated individuals vary widely in their responses to an acute dose of alcohol: Some people experience mainly stimulant-like effects which are generally considered pleasurable, whereas others experience sedative-like effects which are rated more negatively (Holdstock and [name], 1998; King et el 2011). Moreover, the stimulant-like responses to alcohol appear to be predictive of an escalation in use (King 2016). An important question is whether the patterns of stimulant-like and sedative-like subjective effects correspond to differences in brain activation with the drug. We (Weafer et al, 2018) recently reported a good correspondence between stimulant-like subjective response to intravenous alcohol (0.8 g/kg) and activation of ventral striatal brain areas. In the present project, we wish to extend these interesting findings in two ways: i) to examine the dose-relationships between the mood-brain correlations by administering placebo and two doses of alcohol (0.4 and 0.8 g/kg), ii) to investigate the relationship when the drug is administered by the more naturalistic oral route. We propose to assess brain activation patterns in relation to subjective effects using fMRI in a counterbalanced, 3-session, placebo-controlled, double-blind, within-subjects design with placebo, 0.4 g/kg alcohol and 0.8 g/kg alcohol. During an initial drug challenge screening session, 50 potential scanning subjects will receive a single dose of 0.8 g/kg alcohol, to identify individuals who exhibit a pronounced stimulant effect (N=15) or a sedative effect (N=15) from the drug, and only these will participate in the two scanning sessions. We hypothesize that individual variation in the self-reported stimulant or sedative-like effects of alcohol will correspond with variation in activation patterns in reward-related brain regions.

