EPI images will be processed and analyzed using AFNI (Cox 1996), FSL5.0.9 (FMRIB Software Library), and SPM12 (Wellcome Trust Centre for Neuroimaging). The time series will be volume registered to the median image to reduce motion artifact using 3dvolreg within AFNI. Motion outliers will be identified and censored from analyses. Subjects will be excluded if at least one of their scans showed motion >10mm total displacement in any one direction or if more than 50% of volumes within any time point window (see below) were censored. fMRI analyses. Imaging data will be temporally downsampled to the behavioral data by taking a windowed average including the 35 time points before and after the time of the subjective response measurement, resulting in a downsampled dataset at the same temporal resolution as the behavioral data. We chose this relatively long time period because subjective responses are slow-changing, and averaging over a larger window allow for better signal to noise ratio. The windows do not overlap for any time point. The downsampled fMRI data will be voxel wise correlated with the subjective response data (across all time points) using AFNI's 3dfim+, with the resultant coefficients converted to z-scores using Fischer's transformation. The correlation maps will then be coregistered to the participant's anatomical data and warped to MNI space, resampled to 2mm isotropic voxels and smoothed with an 8 mm FWHM isotropic Gaussian kernel.

Further analyses will follow the plan we used in our previous study (Weafer et al, 2019). We compared correlation maps between the time course of subjective response ratings and the time course of BOLD signal following alcohol to those following placebo using paired *t*-tests. In order to control for typical alcohol consumption, we entered average drinks per week

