from the TLFB as a covariate. Based on previous associations between subjective alcohol response and striatal activity, we focused our analyses within three hypothesis-driven anatomically-focused bilateral striatal regions of interest (ROIs): the nucleus accumbens, caudate, and putamen. We also included bilateral primary visual cortex to serve as a negative control ROI. The striatal ROIs were defined via the AAL atlas and created using MARINA (www.bion.de/eng/MARINA.php; Walter *et al*, 2003). The primary visual cortex ROI (Brodmann area 17) was created using the WFU PickAtlas tool (Maldjian *et al*, 2004; Maldjian *et al*, 2003). We extracted parameter estimates/ β weights representing the correlation between BOLD signal and subjective ratings in z-scores from each ROI following alcohol and placebo and conducted paired *t*-tests in SPSS to compare the two drug conditions. We applied a Bonferroni correction across the four ROIs tested, and so the p-value was set at p < 0.0125. We also conducted exploratory, whole-brain analyses of correlations between BOLD signal and stimulation and sedation ratings using SPM12 (cluster-forming voxel-wise height of *p* < 0.001, *k* = 50). Statistical inferences were based on cluster level significance, corrected for family wise error (FWE, *p* < 0.05).

ASL Analysis

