ASL data will be acquired using a pseudo-continuous sequence (TR = 4700 ms, voxel size= 3.4x3.4x5mm, FOV = 220x220x145mm, flip angle = 90 degrees, TE = 13 ms, bolus time = 1800 ms, TI = 3600 ms) with 35 control-label pairs. A proton density (PD) image (TR = 10000 ms, TE = 13 ms, voxel size = 3.4x3.4x5mm) will be acquired and used as a calibration image for cerebral blood flow (CBF) quantification in addition to the T1-weighted structural scan used for registration. Data will be preprocessed and analyzed using FSL analysis tools (Smith et al., 2004). Each data set will be preprocessed using a pipeline including motion correction, registration of ASL to the structural image, partial volume correction and distortion correction. Quantification of CBF will be completed using FSL's BASIL tool (Chapell et al., 2009). CBF will be quantified in units of ml/100g/min using a kinetic model and defaults for the parameters consistent with the formula in the ASL consensus paper (Aslop et al., 2015). For group analysis, quantified CBF images will be normalized to MNI space, smoothed and adjusted to account for individual differences in global CBF and voxelwise within-group ANOVAs will be conducted to assess for drug effects. Voxels showing differential perfusion will be converted to masks and used to interpret drug effects found from fMRI analyses.

Dependent Measures:

• **Subjective Effects.** Participants will complete comprehensive subjective effects questionnaires during the initial baseline session to determine their subjective alcohol profile. They will complete the three questionnaires described below at 15-30 min intervals during the baseline session. During the scanning sessions they will complete only the 5 questions of the DEQ (below) at 5 min intervals.

Biphasic Alcohol Effects Scale (BAES; Martin et al, 1993): 14-item questionnaire on which subjects rated the degree to which they feel subjective stimulant and sedative responses to alcohol on 11-point likert-type scales.

Subjective Effects of Alcohol Scale (SEAS; Morean et al, 2013): also a 14-item questionnaire on which subjects rated the degree to which they feel subjective stimulant and sedative responses to alcohol on 11-point likert-type scales.

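### The group-level BOLD tests compare alcohol with placebo only; no stated test compares the rating–BOLD correlations across the three doses or between the two responder groups

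*Combined protocol and SAP*

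**What the plan says.** **Aims.** The opening Summary of the combined protocol and SAP gives the first extension of earlier work as "to examine the dose-relationships between the mood-brain correlations by administering placebo and two doses of alcohol (0.4 and 0.8 g/kg". The closing Summary proposes to compare responses between 15 subjects with mainly stimulant effects and 15 with mainly sedative effects. Under Design, every scanned subject receives all three conditions in random order.

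**Group-level BOLD analysis** (fMRI Data Acquisition and Analysis). Each session yields a correlation between ratings and BOLD signal, converted to Fisher z. Then: "Further analyses will follow the plan we used in our previous study". The description that follows is in the past tense. Correlation maps were compared with "the time course of BOLD signal following alcohol to those following placebo using paired" t-tests, with drinks per week as covariate. ROI values were tested with paired t-tests "to compare the two drug conditions". On multiplicity: "We applied a Bonferroni correction across the four ROIs tested, and so the p-value was set at p < 0.0125". A further whole-brain analysis is labelled exploratory: "We also conducted exploratory, whole-brain analyses of correlations between BOLD signal and stimulation and sedation ratings using SPM12". None of these states a dose, responder-group or dose × group term.

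**Ratings.** Under Dependent Measures: "During the scanning sessions they will complete only the 5 questions of the DEQ".

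**The concern.** The analysis has two conditions and one sample; the trial has three conditions and two selected groups. If it is followed as written, the two features that the trial adds at some cost, a second alcohol dose and a responder split obtained by challenging 50 people, have no BOLD test attached to them.

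Two things are also left open: which dose is meant by alcohol (0.4, 0.8 or an average), and whether the 30 subjects are pooled or tested by group. The natural patch is to run the same paired test once per dose or once per group. That invites conclusions such as an effect at 0.8 but not 0.4, or in stimulant responders only. Neither pattern is a test of a difference.

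**Working it through.** **1. The plan's own figure.** 0.05 / 4 ROIs = 0.0125, as stated. This allows one contrast per ROI, which fits a two-condition study.

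**2. Two dose contrasts per ROI at the same threshold.** With 0.4 v placebo and 0.8 v placebo there are 4 × 2 = 8 tests. The Bonferroni bound is 8 × 0.0125 = 0.10; if the tests were independent it would be 1 − (1 − 0.0125)^8 = 0.096. Restoring 0.05 needs 0.05 / 8 = 0.00625.

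**3. Assumptions for the power figures.** The documents give no effect size, SD or dropout rate. I assume that a within-person difference in Fisher z between two sessions has SD 1, session errors are equal and independent, tests are two-sided, and there are no dropouts unless stated. Session and drinks terms are not included.

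**4. Paired tests run separately by group.** Suppose both groups have the same effect, 0.8 SD. For n = 15 at 0.0125, the noncentral t (df 14, noncentrality 0.8 × √15 = 3.10) gives power 0.60. The chance that exactly one group is significant is 2 × 0.60 × 0.40 = 0.48, although the groups do not differ.

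**5. Paired tests run separately by dose, all 30 subjects, at 0.0125** (simulation, 60,000 replicates per shape).

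| True effect at 0 / 0.4 / 0.8 g/kg (SD) | 0.8 v placebo rejects | 0.8 significant, 0.4 not |
|---|---|---|
| Linear: 0 / 0.4 / 0.8 | 95% | 62% |
| Plateau: 0 / 0.8 / 0.8 | 95% | 4% |
| Threshold: 0 / 0 / 0.8 | 95% | 94% |

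The 0.8-v-placebo test is blind to shape. The pattern in the last column is common under both a linear and a threshold effect.

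**6. Power of a direct group comparison.** For a 1.0 SD group difference in the 0.8-minus-placebo change, 15 v 15, the noncentrality is 1.0 × √(15/2) = 2.74 with df 28. For an assumed 12 v 12 it is √6 = 2.45 with df 22.

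| Two-sided level | Power, 15 v 15 | SD needed for 80% power, 15 v 15 | Power, 12 v 12 |
|---|---|---|---|
| 0.0125 | 54% | 1.29 | 41% |
| 0.00625 | 43% | 1.40 | 31% |
| 0.003125 | 33% | 1.50 | 23% |

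**7. Drinks per week in a three-dose model.** Write z_ij for subject i at dose j, with a main effect γD_i of drinks per week. In z_i,0.8 − z_i,0 the term γD_i cancels. With complete data a main effect therefore cannot adjust any dose or dose × group contrast. With a drinks × dose term the difference keeps (γ_0.8 − γ_0)D_i, which is what a covariate on a paired difference supplies.

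**8. Error term.** A random subject intercept with pooled error assumes sphericity; a paired t-test does not. In a simulation with assumed session SDs in ratio 0.5 : 1 : 2 over the doses, the pooled-error dose test at nominal 0.625% rejected in 1.5% of null trials. The 0.8-v-0.4 step, read only after that test rejected, did so in 2.2% when those two doses were equal.

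**The case against.** **Following the earlier plan could imply an extension to three doses.** Possibly, but none is written, and both the reference to two drug conditions and the 0.05/4 threshold fit one contrast per ROI.

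**The plan does analyse mood–brain coupling and does contain an ANOVA.** A reader might infer that the mood–brain hypothesis goes unanalysed. The documents do not support that: the per-session correlations address coupling within a session. What is missing is a comparison of those correlations across doses or groups. The ANOVA under ASL Analysis is for perfusion, is within-group, and serves to interpret the fMRI findings, so it does not fill the gap.

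**The in-scanner ratings.** A reader might infer that stimulation and sedation are not rated in the scanner. The Drug Effects Questionnaire entry lists an item on feeling lively and talkative and one on feeling relaxed or sluggish, which are the evident counterparts. Only the explicit mapping and the choice of primary item are missing.

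**The aims need not mean what a demanding reviewer wants.** This stands in part. The protocol speaks of dose relationships, not of separating linear, plateau and threshold shapes, and no stated hypothesis predicts a dose × group interaction; the group aim comes from the closing Summary. Making both the dose and the dose × group test confirmatory is therefore a choice, not a requirement.

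**It is a preliminary, pilot study.** That limits the power to expect and lowers the severity. It does not make a two-condition test an answer to a dose or group question.

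**Conclusion.** The point holds. As written, no BOLD test compares the rating–BOLD correlations across the three doses or between the responder groups, and the alcohol dose and the pooling are undefined. This rests on the text alone.

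The size of the consequence rests on assumed effects: one group alone significant in 48% of trials when both share a 0.8 SD effect, and a family-wise bound of 0.10 rather than 0.05 if two dose contrasts are run at 0.0125.

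It should be fixed before analysis. A reader might go further and infer that the trial cannot meet its aims, or that the open choices will be made after seeing the data. The documents show neither: the necessary data are planned, and nothing in the text indicates an intention to choose late.

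**What to change.** Replace the ROI paired t-tests with one model per ROI on the Fisher-z values from all planned sessions.

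- **Terms:** categorical dose (3 levels), responder group, dose × group, session number, centred drinks per week, and drinks per week × dose. Without the last term the intended control for typical drinking is lost.
- **Error:** unstructured within-subject covariance with a small-sample df correction, or a Greenhouse–Geisser correction, or contrast-specific error terms.
- **Named tests:** the dose test with its steps (0.4 v placebo, 0.8 v 0.4), and the dose × group test. State for each whether it is confirmatory or exploratory.
- **Threshold:** 0.0125 for one confirmatory test per ROI; 0.05 / 8 = 0.00625 if both are confirmatory in four ROIs; 0.05 / 16 = 0.003125 if two ratings are also both confirmatory.
- **Rating:** say which in-scanner items serve as stimulation and sedation, and which is primary.
- **Group factor:** define it by one measure. Experimental Procedure selects on combined BAES and SEAS responses, the closing Summary on POMS Arousal; these must be reconciled.
- **Reporting:** confidence intervals for each dose step and for the group difference. Keep the alcohol–placebo paired contrast as secondary, with the dose named.

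**Cost:** no new data, only wording and analysis. The downsides are less like-for-like comparability with the earlier study, a stricter threshold if both tests are confirmatory, and low power for the group comparison, as tabulated. The closing Summary expects dropouts, which would lower that power further. The protocol should say so plainly.

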number of subjects. More recently, a study used fMRI to show that oral alcohol suppressed brain activity during performance of simple cognitive tasks (Horn et al. 2006). However, few studies have examined the localized effects of alcohol in the brain in relation to its self-reported subjective effects. As noted above, we recently (Weafer et al, 2018) examined fMRI BOLD response after intravenously administered alcohol. As expected, we found that alcohol produced stimulant-like effects in a subset of individuals, and using region of interest analyses we showed that the time course of stimulation correlated with BOLD signal in the striatum. In the present study we aim to extend this finding i) using more naturalistic, oral administration of ethanol, ii) using two different doses of alcohol, and iii) adding ASL measures to monitor changes in blood perfusion to inform interpretation of neural activation changes. We hypothesize that inter-individual variation in the self-reported subjective effects are expected to be associated with increases in the mesolimbic system (related to dopamine activity), whereas sedative-like effects are expected to be more associated with areas rich in GABA.

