Design: We will measure individual differences in brain activity after two doses of alcohol (0.4 g/kg, 0.8 g/kg) or placebo using fMRI. Participants (N=50) will first be pre-selected ('ascertained') based on their responses to a single dose of alcohol (0.8 g/kg) in the behavioral laboratory. Individuals who exhibit either a clear stimulant-like response or a clear sedative-like response to alcohol will be invited to continue to the three fMRI scanning sessions. From the 50 participants tested, we will select 15 stimulant responders and 15 sedative responders. The three imaging sessions will be at least 72 h apart. At each session, subjects will receive the beverage containing alcohol or placebo, and then be placed in the fMRI scanner. Order of the three drug conditions (0, 0.4 and 0.8 g/kg ethanol) will be randomized and the drug will be administered under double-blind conditions. Immediately before and after the scan, subjects will complete standardized questionnaires to assess mood and subjective drug effects. We hypothesize that stimulant-like subjective effects will be associated with increases in activation in the striatum and regions related to the mesolimbic dopamine circuit. To minimize variability related to body composition and cycle phase, only males will be recruited for this preliminary study. Later, we will extend the study to include female participants.

Subject Recruitment and Screening

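### Visual cortex is the negative control, but no planned test compares the striatal change with the visual-cortex change, so region-specificity could be judged only from one test being significant and another not

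*Combined protocol and SAP*

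**What the plan says.** The ROI plan is in 'fMRI Data Acquisition and Analysis'. It is in the past tense because it is carried over from the group's previous study, which the text says this study will follow. For each subject and condition it extracts values "representing the correlation between BOLD signal and subjective ratings in z-scores from each ROI following alcohol and placebo" and compares the two conditions with a paired t-test in each ROI. Three ROIs are striatal (accumbens, caudate, putamen). Of the fourth it says: "We also included bilateral primary visual cortex to serve as a negative control ROI". The threshold is stated as: "We applied a Bonferroni correction across the four ROIs tested, and so the p-value was set at p < 0.0125".

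No section gives a striatum-versus-visual-cortex contrast, an ROI-by-drug interaction or an equivalence test, and none says how the control's result will be used. The Design section hypothesises that "stimulant-like subjective effects will be associated with increases in activation in the striatum and regions related to the mesolimbic dopamine circuit".

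Two other analyses bear on specificity. The whole-brain maps are labelled exploratory and are cluster-thresholded. Under 'ASL Analysis' the plan says: "Voxels showing differential perfusion will be converted to masks and used to interpret drug effects found from fMRI analyses".

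**The concern.** A negative control region serves to show whether an effect is general rather than specific to the target. With four separate tests and no comparison between regions, it can suggest specificity only by failing to reach significance. A significant result in one region and a non-significant one in another is not evidence that the regions differ; with modest power the pattern arises easily when the true change is the same in both.

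A general effect is plausible here. Ratings and BOLD are correlated over one session after an acute dose, so any signal that follows the drug's time course can correlate with ratings that follow it too. Ratings that vary more after alcohol, around one relation shared by all regions, would also raise the correlation everywhere. The Background section shows that the investigators have such changes in mind: one aim is "adding ASL measures to monitor changes in blood perfusion to inform interpretation of neural activation changes".

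At stake is the interpretation. A correlation change that is also present in visual cortex could be read as particular to the striatum. The whole-brain maps do not settle this, because they too compare thresholded results between places. The ASL masks show where perfusion differs, not whether the correlation change is larger in striatum.

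**Working it through.** **1. The plan's own figure.** 0.05 / 4 = 0.0125, as stated. The family-wise 0.05 is implied. The documents give no power figure for the ROI tests.

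**2. Power of the control's test.** Inputs: 30 scanned subjects (15 + 15, Design) and about 60 / 5 = 12 ratings per scan (Experimental Procedure). Assumptions: pooled groups, two-sided test, no between-person variation in the true correlation difference (such variation would lower power).

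- Variance of one Fisher z: 1 / (12 − 3) = 1/9.
- SD of a within-subject difference: √(2/9) = 0.471.
- SE of the mean difference: 0.471 / √30 = 0.086.
- With an assumed loss to 24 subjects and 10 ratings: √(2/7) / √24 = 0.109.

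Power at 0.0125 from the noncentral t distribution:

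| True Fisher-z difference | 30 subjects, 12 ratings | 24 subjects, 10 ratings |
|---|---|---|
| 0.15 | 20% | 11% |
| 0.20 | 38% | 22% |
| 0.25 | 60% | 36% |

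In standardised units (mean difference over its SD), the control at n = 30 misses a shift of 0.3, 0.5 or 0.7 in 83%, 46% or 13% of trials. At n = 15 (one responder group) it misses 93%, 78% or 54%.

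**3. Hand check of the misleading pattern.** Suppose all four ROIs have the same true difference, each test has 38% power, and errors are independent. One given striatal ROI is significant and visual cortex not in 0.38 × 0.62 = 24% of trials. For at least one of three striatal ROIs the figure is (1 − 0.62³) × 0.62 = 47%. Correlated errors between ROIs lower this.

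**4. Simulation under one shared relation.** Model: autocorrelated ratings (coefficient 0.7); BOLD = slope × rating + unit noise in four ROIs, with the same slope in every ROI and condition. Assumed values, as the documents give none: slopes 0.01-0.04 noise SD per mm, noise correlation between ROIs 0-0.6, rating SD 20 mm after alcohol against 15, 10 or 4 mm after placebo. There are 30 subjects and 12 ratings, and the drinking covariate is left out.

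- At least one striatal ROI significant and visual cortex not: about 0-42% of trials. It is near 0 where the shared effect is so large that visual cortex is almost always significant too.
- In variants where the correlation difference is itself near zero (compressed placebo ratings, higher BOLD gain, drift shared by both conditions): about 2%.
- Judging visual cortex at 0.05 instead of 0.0125: still up to about 30%.

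**5. With the contrast added.** The contrast is (striatal z − visual-cortex z) after alcohol minus the same after placebo. If its true value is zero, three tests at 0.0125 counted only in the positive direction give at most 3 × 0.0125 / 2 = 1.9%. In the simulation, a striatal result with a positive contrast occurs in about 2% of trials or fewer.

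**6. Unequal noise.** Noise lowers a correlation, so one shared relation gives a smaller Fisher-z change in a noisier region. With visual cortex 1.5, 2 or 3 times as noisy as striatum (slopes 0.02-0.04, noise correlation 0.3), a brain-wide relation still gives a striatal result with a positive contrast in about 1-31%, 2-63% or 3-89% of trials. The documents give no ROI noise levels.

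**7. Power cost when the relation is truly striatal only** (slope 0.02, noise correlation 0.3). The chance of a specificity claim falls from 50% to 22% at 20 v 10 mm, and from 91% to 69% at 20 v 4 mm.

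**The case against.** The strongest reply is that the plan never says it will claim specificity from a significant striatum and a non-significant visual cortex. Its hypothesis is an association with striatal activation, not striatum greater than visual cortex. That is correct: a reader might infer that the plan adopts this decision rule, and the documents do not support that. What stands is narrower. A region named as a negative control has no use except to judge specificity, and the plan supplies no test that can do so.

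A second reply is that how often the pattern misleads is unknown. This also stands. The documents give no slopes, rating SDs, noise levels or effect sizes, and the simulated range includes zero. A reader might infer that the control usually misses a brain-wide effect. That holds for small shifts and fails for large ones: at n = 30 the control misses only 13% at a standardised shift of 0.7.

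A third reading blames the Bonferroni threshold for weakening the control. It contributes, but loosening it to 0.05 leaves most of the problem. The missing between-region test is the point.

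Finally, the contrast is not a complete safeguard, because its protection depends on similar noise across ROIs. This is a real limit, and the reason to report noise beside it.

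**Conclusion.** The concern holds in a conditional form. The plan names a negative control but contains no test that the striatal change exceeds the control's, and neither the exploratory maps nor the ASL masks fill that gap. Under a relation shared by all regions, the apparent striatum-only pattern occurs in about 0-42% of simulated trials, depending on assumed slopes, rating spread and noise correlation. The added contrast brings this to about 2% if ROI noise is similar, but not otherwise.

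The four planned tests are not shown to be invalid: the Fisher-z comparison is sound for the within-region question it asks. What changes is what may be concluded from them. A striatal result alone supports a correlation difference in striatum, not one that is specific to striatum.

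**What to change.** Keep the four planned tests and p < 0.0125. For each striatal ROI add a paired t-test of (striatal z minus visual-cortex z) after alcohol minus the same after placebo, with the same covariate and threshold. Use the same dose comparison, DEQ item and subject group as the striatal test it accompanies, and state these in the plan, since there are two active doses, five in-scanner items and two responder groups.

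- Call a difference region-specific only if the striatal test and its contrast are both significant and positive. Otherwise write: *correlation differs in striatum; not shown to differ from visual cortex*.
- If visual cortex is also significant, report that, and describe the effect as larger in striatum than in visual cortex, not as absent in visual cortex.
- Report all four ROI estimates with confidence intervals, and rating and BOLD SDs by ROI and condition.
- If the contrast is positive but visual cortex is clearly noisier, or is itself significant, say that unequal noise may explain the result.

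Requiring visual cortex to be non-significant as well is not advised. In a simulation with a striatal slope three times that of visual cortex (0.08 v 0.027, rating SD 20 v 4 mm), that extra condition allowed the specificity claim in only about 9% of trials, against nearly 100% for the striatal test plus the contrast.

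The cost is a few lines of analysis on values already extracted, with no new data. The striatal tests keep their power; the specificity claim loses power, as shown in the working.
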